We plan to integrate other VA tools currently being rolled out to patients across the VHA network. Two ideas under development are (1) My HealtheVet that will include secure message communications between the care manager and patients, and (2) Facebook and other social media tools to disseminate educational materials and upcoming support group sessions to veterans enrolled in the intervention arm of CHAPS.

As part of total care management, if a veteran in the intervention group states that he/she has a caregiver during the administration of the CHAPS assessment tool, we will send the veteran a *CHAPS Intervention Caregiver Support Packet* (Appendix 7) that will contain assessment questions regarding depression, strain, social isolation, and overall health. Assessment questions will contain scoring guides to assist the caregiver in determining if there is a potential problem to seek self-directed support and assistance. The packet will also contain contact information for agencies that provide caregiver resources such as the Caregiver Resource Center. This packet is to be given to the caregiver by the veteran and is completely voluntary. Caregivers are not subjects of the study; in other words, the packet will not be collected or used by the study.

Research Design and Methods 2 – "Usual Care" Randomization Arm Description. Veterans randomized to the usual care arm will continue to receive care they would have received if they had not enrolled in the study. To minimize potential bias from participants' awareness of randomization arm assignment²⁵, we will provide to all study participants (both intervention and usual care arm participants) a brief educational handout on Parkinson's disease that is available in the VA's "Healthwise for Life" handbook (Appendix 8)²⁶. This information includes a definition of PD, its symptoms, and several suggestions for managing PD such as medications and regular exercise. Since the CHAPS kiosk will be located publicly in the Movement Disorder clinic, it will not be withheld from any veterans who wish to use it. Also, the PADRECC Facebook page will be made available to all veterans.

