Figure 3. Enrollment sample sizes for achieving analytic sample sizes, across a range of effect sizes and retention rates.

Note that the power analysis is almost certainly conservative in that the multivariate model used to formally evaluate study group differences has the typical effect of reducing residual variance of the model and improving the ability to detect group differences.

Research Design and Methods 5 – Study Variables

Research Design and Methods 5 - Primary Outcome (dependent variables) will be adherence to PD guideline implementation (care processes) that were identified by the VISN 22 and community-wide NRI pilot-study Task Force as high priority quality indicators for guideline implementation, out of prior PD guidelines developed in VA and other sources as described in the background. These guidelines cover 9 categories: Communication, Education and Continuity; Reporting; Diagnosing PD; Medication use; Motor symptom management; Management of non-motor PD complications; Non-pharmacological approaches; Palliative care; and Health maintenance. The primary outcome measure will be based on the proportion of eligible subjects receiving each recommended care indicators and calculated as a mean per patient of applicable care processes adhered to. Some care processes will be indicated only if triggered by an identified problem. For

example, referral to a primary care physician for evaluation and treatment of depression is only indicated if a depression screen is positive. Some survey questions will measure care processes, specifically regarding veteran education, counseling, referral and other practices for which medical charts are not always accurate, so the data sources for this primary outcome will be both medical record abstraction and telephone survey of study participants. The proportion of applicable recommendations followed for each veteran will be computed and aggregated to the two group levels (intervention and usual care arms).

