Health Services Utilization. Physician visits, emergency department visits, hospital admissions, nursing home admissions (distinct from respite care), home care services, and pharmacy data for the period 12 months preceding enrollment and during the 18 months (or 24 months for the first 204 enrollees) of the intervention will be collected from the VISN-22 Data Warehouse. The VISN-22 Data Warehouse contains detailed clinical data about Veterans Administration care (including hospitalizations, clinic visits, prescribed medications and demographics) for 5 hospitals and 28 community-based clinics within the VA Desert Pacific Healthcare Network. The database includes admissions to non-VA hospitals if the VA reimburses those hospitals for the care delivered. CHAPS investigators will prepare a query to the VISN-22 Data Warehouse in Year 4 for these data on study participants.

Missing-data, respondent dropout, interviewer bias.

Missing-data: Data collected from medical record abstraction and administrative records will be complete and will not contain missing data. All survey data is collected by immediate computer entry using a computer software program (Microsoft Infopath or Microsoft Access) that will be programmed to incorporate appropriate skip patterns and flag invalid entries as the RA administers the telephone survey. This computer based data collection will produce a clean dataset with minimal missing data and no out-of-range entries. Periodic data quality checks will be carried out by the data manager to identify systematic patterns of missingness that may occur during data collection.

Respondent dropout: In order to reduce dropout due to the participant being unreachable, we will collect multiple contact phone numbers at enrollment and implement tracking procedures for contact attempts by the study team as outlines in the human subjects section. A toll-free number will be available for participants to reach the research staff and flexible interview times will be offered to participants. If necessary, surveys can be completed over multiple contacts with the participants.

Interviewer bias: Study research assistants that conduct the telephone surveys, and the nurse abstractors who conduct the medical record abstractions will be blinded to the intervention status of participants.

Data Management and Quality Control. Research subject level data will be maintained in 3 separate files:

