Research Design and Methods 7 – Strategy for Data Analysis. All analyses will follow the intention-to-treat principle in that participants are included in the analyses regardless of the level of exposure to the intervention activities. In order to accomplish this analysis in patients who drop out of the study, we will employ a conservative imputation method such as last-value-carried-forward (LVCF). We will consider a P value less than or equal to 0.05 as statistically significant.

Specific Aim #1. Primary Outcome: Guideline Adherence. Guideline adherence will be determined by de-identified medical record and caregiver survey data. Outcomes are expressed as a percentage of applicable guidelines followed, which can be treated as continuously-scaled. In Table 4 of this application are examples of PD indicator process measures. Overall guideline adherence will be calculated as the mean percentage of eligible guidelines per patient that was adherent. Each of the 38 guidelines will also be analyzed individually.

All multivariate analyses will be preceded by bivariate analyses to describe relationships between key variables. First, descriptive statistics comparing the two arms on sociodemographic and clinical characteristics

(such as duration of PD) and on study outcome measures at baseline, using two-sample t-tests for continuous variables and χ^2 tests for categorical variables. We'll also compare baseline characteristics between participants who complete follow-up surveys and participants who do not complete follow-up surveys. Participants who do not finish the 18-month follow-up (or 24 months for the first 204 subjects; see below) due to bereavement or loss to follow-up will be excluded from the analyses but sensitivity analyses will include these participants.

An intention-to-treat analysis on all guideline adherence over time will be conducted using linear regression (or logistic regression when analyzing guidelines individually) with sampling weights using the sandwich variance estimator (robust variance estimator and Huber correction)⁵⁴⁻⁵⁵ as implemented in Stata, version 11. Intervention status, indicator variables for site and corresponding baseline measure will be included as independent variables in all models. Other potential important covariates will be selected in advance of data analysis to be included in the model.

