Although we anticipate modest attrition in this sample, we will use attrition weights for dependent variables obtained from the survey. Attrition weights will be derived using a logistic regression of the response status (completed study vs. not completed) on predictors, including demographics. The response probability will be predicted for each subject according to a fitted model. The weight will be the reciprocal of response probability.

The analysis also must account for the gap in the intervention over more than 6+ months for the subset of the first 204 patients enrolled in the trial and randomized to the intervention arm. Because of this, a 24 month survey was added to the study for all 204 of these individuals. The remaining 96 subjects who will be enrolled to obtain the final target enrollment of 300 but who will not experience this gap in the intervention will be followed for the pre-defined 18 months. In order to combine both of these "cohorts" into a complete analysis, a variable will be incorporated into the regression models to reflect the period of time the subject was off the intervention. For the subset out of the first 204 patients who were randomized to the intervention arm, this variable will take on a value of the number of months for this period; while for the second cohort of 96, this variable will take on the value of 0. (Also, any subject in the control ("usual care") group in either cohort will receive a value of 0 as well). This will be used as a linear adjustment variable to account for this anomaly in the way the intervention was administered, by incorporating it into a multiplicative interaction effect with intervention status. If this term is significant, then it will indicate that the delay of intervention affects the outcomes. The main effect of intervention status will remain as a separate term in the model.

Specific Aim #1. Secondary Outcome Measures:

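### The primary adherence score pools chart items with self-report from participants who know their arm, and no summary by data source is planned, so the composite alone cannot show whether a benefit depends on the self-reported items.

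*Combined protocol and SAP*

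**What the plan says.** Research Design and Methods 5 (Primary Outcome) builds the score from two sources: "so the data sources for this primary outcome will be both medical record abstraction and telephone survey of study participants". It explains the survey part as follows: "Some survey questions will measure care processes, specifically regarding veteran education, counseling, referral and other practices for which medical charts are not always accurate". It gives neither the number nor the list of indicators scored that way.

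Research Design and Methods 7 (Strategy for Data Analysis) merges everything into one figure: "Overall guideline adherence will be calculated as the mean percentage of eligible guidelines per patient that was adherent". It adds an item-level analysis: "Each of the 38 guidelines will also be analyzed individually". The same paragraph describes the source differently: "Guideline adherence will be determined by de-identified medical record and caregiver survey data". Yet the intervention description in Methods 2 says "Caregivers are not subjects of the study", and the packet sent for caregivers is not collected by the study.

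On blinding, the design overview calls the trial single-blinded. The paragraph on interviewer bias names telephone interviewers and chart abstractors as the blinded staff. The usual-care description accepts that participants' awareness of their arm may cause bias, and answers it with the same short handout for both arms.

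On missing data, the plan says: "Data collected from medical record abstraction and administrative records will be complete and will not contain missing data". For the survey it says: "we will use attrition weights for dependent variables obtained from the survey".

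**The concern.** Education, counselling and referral are what the nurse care manager provides, and they are also what participants are asked to report. A veteran in regular telephone contact with a study nurse may recall or credit such care more readily than a usual-care veteran who received the same care elsewhere. A blinded interviewer does not blind the respondent. If recall differs by arm, the survey items move the composite even when delivered care is the same.

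The trial is meant to inform VA decisions on adopting the model. Readers of a positive result will ask whether it also appears in the items scored from records, and the planned primary analysis does not answer that.

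The sources also differ in missingness. The plan treats chart data as complete, while survey data are lost with dropout. The main analysis leaves out participants who do not finish follow-up and brings them back only in sensitivity analyses, so chart data already in hand can go unused because a survey is missing.

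**Working it through.** **1. The plan's own figure.** Table 3 gives 235, 173 and 133 per arm for effect sizes 0.3, 0.35 and 0.4 at 90% power. A two-sample t-test calculation at two-sided alpha 0.05 gives 234.5, 172.5 and 132.3, which round up to the same numbers. The point does not rest on a sample-size error.

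**2. Is there an analysis by source?** Four places could hold one:
- The primary-outcome section names both sources but gives no split.
- The primary analysis fits one linear regression to the composite and logistic regressions to single indicators.
- The sensitivity analyses listed under the secondary outcomes are carry-forward, 6-month data only, 12-month data only and change within arm.
- The paragraph on attrition weights separates survey variables from others, but does not say how a score built from both is treated.

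None gives a source-level score, an indicator-to-source list, or a rule for when chart and survey disagree.

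**3. Illustration of size.** Let f be the share of applicable indicators scored from the survey, b the extra percentage points reported as met in the intervention arm with no true difference, and SD the standard deviation of the per-patient score. Then

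- spurious difference = f × b
- standardised shift d = f × b / SD
- chance of p ≤ 0.05 = two-sample t-test power at d with 133 per arm.

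The documents give none of f, b or SD. All three are assumptions, and so is the direction of the bias.

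| f | b (points) | SD (points) | f × b | d | Chance of p ≤ 0.05 |
|---|---|---|---|---|---|
| 10% | 5 | 20 | 0.5 | 0.025 | 5.5% |
| 10% | 5 | 15 | 0.5 | 0.033 | 5.8% |
| 25% | 10 | 20 | 2.5 | 0.125 | 17% |
| 25% | 10 | 15 | 2.5 | 0.167 | 27% |
| 50% | 10 | 15 | 5.0 | 0.333 | 77% |
| 50% | 10 | 12 | 5.0 | 0.417 | 92% |

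To imitate the whole design effect of 0.4 at SD 15, b must equal 0.4 × 15 / f = 6 / f. That is 60, 24 or 12 points for f of 10%, 25% or 50%. With a small survey share the bias could hardly explain a result of the planned size; with a large share it could.

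**4. Would a chart-only score gain power?** At d = 0.4, power is 90% with 133 per arm and 93% with 150 per arm. But a score from fewer indicators need not have the same standardised effect. At 150 per arm, power is back to 90% once the chart-only effect is about 0.376. No power gain should be claimed.

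**The case against.** The strongest reply is that the plan already analyses each of the 38 indicators. Once sources are known, anyone can see where an effect lies. That stands in part, and a reader who inferred that reporting and care can never be told apart would be wrong. But no source map is stated (one may exist in the survey appendix or abstraction tool, which are not in the supplied text), triggered indicators apply only to subsets of participants, and no multiplicity rule is given. If the 38 tests were independent at 0.05, the chance of at least one false positive would be 1 − 0.95^38 = 86%.

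Second, source is mixed up with type of care. The survey items cover what the nurse delivers, so a working intervention may have its largest true effect there. This stands in full. It is tempting to treat a survey-only benefit as reporting bias and refuse to call it improved care; the documents do not support that rule, which could throw away a real effect.

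Third, charts are not a neutral yardstick. Methods 2 has a summary of the CHAPS care plan pasted into CPRS, the system the abstractors read. Intervention charts may therefore document more, and may reveal the arm. This also stands and shapes the fix.

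Fourth, a reader might infer that a chart score covers all 300. The statement on completeness does not establish that: deaths and disenrolment are expected, some enrolled veterans may be removed, and their records cover a shorter window.

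Finally, Care Partners may help veterans answer, so some proxy input exists. The word caregiver may therefore be only loose wording, but it still conflicts with the primary-outcome section.

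**Conclusion.** The concern holds in limited form. One composite pools chart items with self-report from participants who know their arm, and no source-level summary is planned. The composite alone therefore cannot show whether a benefit depends on the self-reported items, and the item-level analyses fill that gap only in part. The naming of the survey respondent is inconsistent between the outcome and analysis sections.

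The size is not established. Depending on assumed inputs, the false-positive chance runs from about 6% (10% share, 5 points, SD 15 to 20) to a range of about 17% to 92% (25% to 50% share, 10 points, SD 12 to 20). The documents do not say which case is nearer, which is itself a reason to list the sources. Nothing here shows that bias will occur or that the composite is the wrong primary outcome. The point is worth acting on because the remedy is cheap and affects what a positive result can support.

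**What to change.** 1. In Strategy for Data Analysis, reconcile the caregiver-survey wording with the participant telephone survey named in the primary-outcome section.
2. Before unblinding, assign each of the 38 indicators to chart or survey, and state the rule for any indicator where both sources exist and disagree.
3. Keep the composite as primary. Pre-specify two supporting analyses with the same model, each adjusted for its own baseline value:
   - a chart-only score in all randomised participants with abstractable records over a defined window, including how deaths and withdrawals are handled, run with and without CHAPS-authored CPRS notes;
   - a survey-only score with the attrition weights already planned for survey outcomes.
4. Report both beside the composite. State in advance that a benefit confined to survey items may reflect real nurse-delivered education and counselling or differential reporting, and that the data cannot fully separate the two.

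The cost is an indicator list, two supporting scores and a repeat of the chart model without CHAPS notes. No new participant data are needed, though abstraction must flag which entries come from CHAPS notes. Each score uses fewer indicators than the composite, so its interval will probably be wider; neither should be presented as a second primary test.
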